Clinic Recruitment:

Newly referred patients to the interdisciplinary clinics will be pre-screened for eligibility prior to their first clinic visit by a study team member. The patients who meet eligibility criteria will be contacted via phone by a study team member. During the call, we will briefly introduce the study aims, intervention, and different groups. We will request the youth and family to consider participation and will thoroughly discuss the study at the consent

(baseline) visit. The study team member will obtain the eligible participants' email address and send them a recruitment flyer via email if interest is expressed.

AltaMed referral/recruitment:

Patients that meet age and/or BMI criteria, will be provided with study recruitment material and/or the patient will be referred to the study team by AltaMed providers/staff. The study team will acquire patients name, age, BMI (if available) and contact information.

Initial Visit (all participants):

1. Study team member will meet in person/virtually with eligible participants and provide details about the study procedures, obtain written/electronic permission from one parent/legal guardian and assent from minor participants or consent from participants 18 years of age and answer any questions the participants and their parent/legal guardian may have.
- a. Upon obtaining consent from one parent or guardian and assent from each youth to participate in the study, participants will be randomized to one of 3 intervention arms (**AppCoach vs. App vs. Clinic**). If participant is consented via mail, the randomization will occur during the second part of visit 1. The participant will have the option of curbside pickup or mailing of study supplies. If consenting via mail, the study team will mail supplies to participant after receiving signed consent back. If consenting electronically via REDCap or DocuSign, study team will mail study supplies day of consent if possible.
2. All consenting participants will complete a battery of surveys (Refer to Measurements section).
 - a. Youth:
 - i. Yale Food Addiction Scale¹⁹
 - ii. The Center for Epidemiologic Studies Depression scale²⁰
 - iii. The Perceived Stress Scale²¹
 - iv. Behavior Rating Inventory of Executive function²²
 - v. Binge Eating Disorder Screener²¹
 - vi. Physical Activity Questionnaire
 - vii. Satisfaction Survey
 - viii. Food Craving Questionnaire
 - ix. The Adolescent Self-Regulatory Inventory (ASRI)²³

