 - x. Short form health survey form (SF-12)
 - xi. EQ5-D
 - xii. Stages of Change Questionnaire in Weight Management (S-Weight)

b. Parents:

- i. Demographic Screen
- ii. Health Encounters
- iii. Parent Satisfaction Survey

Outcomes:

	0	3	6	12	18
Study Visit Window of Completion		+/- 2 weeks	+/- 2 weeks	+/- 4 weeks	+/- 4 weeks

Covariates:

Demographic Information	x				
Youth's Perceived Stress Score	x	x	x	x	x
Family Member's BMI	x			x	x

Primary Outcomes:

BMI Status Change- %BMIf95	Height, Weight, zBMI,	x	x	x	x	x
-------------------------------	-----------------------	---	---	---	---	---

Secondary Outcomes:

Adherence-	x	x	x	x	x	
Satisfaction- Satisfaction Survey	x	x	x	x	x	
Fasting Lab Tests-	x		x		x	
Cost Analysis- Encounters*	Health Care	x	x	x	x	x

Mediators:

Addictive eating qualities- YFAS and FCQ	x	x	x	x	x
Self-Regulation- ASRI	x	x	x	x	x
Executive Function- BRIEF 2	x	x	x	x	x

*An official Health Care Encounters questionnaire will be completed by the parents at in-person/WebEx study visits at 0, 3, 6, 12, and 18 months post consent. Additionally, all participants will receive a call monthly from a study team member during the study period. In these calls weight outcomes, barriers and any interim health encounters (physician visits, diagnosis, medication prescribed etc.) occurred in the previous 4 weeks will be assessed.

3. All consenting participants:

- a. AppCoach and AppAlone arms will receive:
 - i. Loaned iPhone (app is iOS compatible only) if the participant does not already have one
 - ii. Wireless Bluetooth body weight scale
 - iii. Digital food scale
 - iv. Measuring tape (if participating virtually)
- b. In Clinic arm will receive:
 - i. Digital body weight scale
 - ii. Measuring tape (if participating virtually)
- c. Participants in the AppCoach and App arms who require an iPhone will be loaned an iPhone and accessories (including protective case), with an AT&T service plan for the 6-month intervention of the study that includes: unlimited texting, unlimited plan, unlimited voice calls to and from other cell telephones, 700 voice call minutes for calls to and from landlines, unlimited night and weekend calls to and from landlines, International calls or texts including Canada are NOT allowed and not covered. iPhones will be returned at the completion of the intervention (visit 3: 6-month follow-up visit/mail equipment back to study team).

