- d. One parent will complete the above-mentioned questions and have their height, weight and BMI measured/self-reported at consent and at 18-month follow up (end of study).

3. AppCoach and AppOnly Participants:

- a. Each participant will be registered with their email address via a computer and then login with the app.
- b. Participants will weigh-in on a scale in a private area and enter weight data into their iPhones. Participants will weigh themselves and their food daily. This information will be automatically synced (entered) into the app. However, if the wireless scales are not used, they will need to enter the information manually into the app.
- c. A study team member will go through each section of the App and have participants enter data.
- d. Follow-up: participants will schedule in-person/WebEx study visits at 3, 6, 12 and 18 months. Participants will also have the option of conducting visits virtually via WebEx and/or receiving survey links via email directly from REDCap.
- e. AppCoach participants will also schedule weekly 15-minute phone meetings with a coach in addition to follow up study visits in-person/WebEx visits at 3, 6, 12 and 18 months.

4. In Clinic Participants:

- a. Each participant will attend a multi-disciplinary in-clinic or WebEx intervention consisting of 6 sessions (120 minutes +/- 30 minutes); one session per month for 6 months.
- b. They will meet with several members of the provider team throughout the intervention: physical therapist, psychiatrist, Registered Dietitian, health educator, physician and research team.
- c. Participants will be weighed or provide a self-reported weight at every session and follow up visits
- d. Participants will have the option of weighing themselves daily.
- e. Follow-up: participants will attend in person/WebEx follow-up visits at months: 3, 6, 12, and 18
- f. Participants will be provided a KNF newsletter for sessions 1-6. The newsletters summarize what was discussed during the session they attended. They will also be provided with a height and weight measurement tool. The newsletter and tool will be emailed or texted.

5. Research Blood Draws (all arms):

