- a. Fasting lab results at enrollment are needed to determine baseline values. Participants that were referred to a weight management clinic at any of the participating sites may have had these labs drawn as part of their routine care. These results will be abstracted from the medical record if they are within 8 weeks of consent date. However, a research blood draw will be done at enrollment if these labs were not done as part of the participant's routine care. If the consent visit takes place virtually/by mail, the participant will be expected to travel to CHLA for a baseline research blood draw.
- b. All arms will have a follow up research blood draw at months 6 and 18.
- c. Each research blood draw will collect approximately 5 mL (1 teaspoon) of blood via venipuncture that will be used for the following testing: HbA1c, Total Chol, LDL, HDL, TG, AST/ALT, Glucose and insulin.

6. All participants

*Visit 1: if consenting via mail, these procedures will be completed at the 2nd session as visit 1 will be split in 2

** Each participant will have the opportunity to earn up to \$200 in gift cards for participation in this study: up to \$50 for participation in the intervention at 3 and 6 months and \$50 for going to the last 2 study visits (at 12 and 18 months). The amount of payment will be based upon how much of the intervention the participant completes.

***Visit 2 and 3 must occur within a 4-week period (+/- 2 weeks from the 3- or 6-month date) and Visits 4 and 5 must occur within an 8-week period (+/- 4 weeks from the 12- or 18-month date).

Study Visit Schedule for Group 3 (In-Clinic) (total visits = 9)

*Visit 1: if consenting via mail, these procedures will be completed at the 2nd session as visit 1 will be split in 2

The youth participants in this group will also earn up to \$50 at 3 months (visits 4) and 6 months (visit 7) for participation in the 6-month intervention and \$50 for completion of study visits 8 and 9.

The table below depicts the assessment time points and key measures.

Month	0	3	6	12	18
Covariates					
Co-Morbidities, race/ethnicity, household composition, socioeconomic status, and previous weight loss programs completed	x				
Primary Outcomes (Aim 1)					
Height, Weight, zBMI, %BMIp95	x	x	x	x	x
Secondary Outcomes / Mediators (Aims 2, 3)					
Youth Surveyed: Yale Food Addiction Scale-Children	x	x	x	x	x
CES-D	x	x	x	x	x
Perceived Stress Score	x	x	x	x	x
BRIEF 2	x				
ASRI	x	x	x	x	x
Food Craving Questionnaire	x	x	x	x	x

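### For in-person and electronic consent the plan randomises ahead of the baseline surveys and height/weight, with no blinding described, and no rule makes baseline data a condition of allocation.

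*Combined protocol and SAP*

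**What the plan says.** The Initial Visit (all participants) section sets the time of randomisation in item 1a: "Upon obtaining consent from one parent or guardian and assent from each youth to participate in the study, participants will be randomized" to one of three arms. The same item makes one exception: "If participant is consented via mail, the randomization will occur during the second part of visit 1". The footnote to the visit schedule adds that "if consenting via mail, these procedures will be completed at the 2nd session as visit 1 will be split in 2". Neither says which comes first in that second session.

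The other baseline steps follow in the list. Item 2 reads "All consenting participants will complete a battery of surveys". Item 3 lists equipment by arm: the app arms receive a "Wireless Bluetooth body weight scale", a food scale and, if needed, a loaned iPhone, while the Clinic arm receives a digital body weight scale. Virtual participants in every arm also receive a measuring tape. For electronic consent, the "study team will mail study supplies day of consent if possible". The start-up weigh-in is written as a step for the app arms only: "Participants will weigh-in on a scale in a private area and enter weight data into their iPhones". Under Research Blood Draws, chart results within 8 weeks of consent may serve as baseline labs. Otherwise, after virtual or mail consent, "the participant will be expected to travel to CHLA for a baseline research blood draw".

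Under Anthropometric Data, height and weight are taken by staff in person and self-reported at virtual visits. The Randomization and Blinding section withholds only the block size, and only from the investigator.

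**The concern.** The primary outcomes are changes from baseline in zBMI and %BMIp95, and the Statistical Analysis section compares the week-24 change in %BMIp95 between arms by ANOVA. A baseline reported after the youth knows the arm can be coloured by that knowledge, for example by disappointment, enthusiasm or the wish to show progress. If this differs on average between arms, randomisation no longer protects the comparison.

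Two further consequences follow.

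- CES-D, PSS, BRIEF-2, YFAS-c and BEDS-7 scores enter the regression models. Where baseline values are used (the only option for BRIEF-2 if, as the Measurements section says, it is collected at baseline only), they are no longer clean pre-randomisation covariates.
- The analysis is intention-to-treat with last observation carried forward. That method cannot create a baseline that was never taken, and no rule covers a randomised youth without one.

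**Working it through.** **Step 1. Order of events by consent route.**

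| Route | Randomisation | Baseline surveys and height/weight |
|---|---|---|
| In person | on consent (item 1a) | listed afterwards |
| Electronic | on consent (item 1a) | listed afterwards; height and weight self-reported if the visit is virtual |
| Mail | second part of visit 1 | same session; order not stated |

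**Step 2. Is the arm likely to be known?** The documents do not say when a family is told. Two facts suggest early knowledge. The equipment differs by arm and, with electronic consent, is posted the same day if possible, so staff need the arm in order to pack it. Under Coach Training Procedures, the coach contacts AppCoach youths at enrolment.

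**Step 3. How a baseline shift enters the result.** Change = follow-up − baseline. If mean baseline reporting error differs between two arms by b points and follow-up is reported without error, the estimated difference in mean change is wrong by b.

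**Step 4. Inputs for scale.** From Power and Sample Size Estimates: AppCoach versus Clinic, difference 4.08 points of %BMIp95, effect size 0.625, stated power 92%; AppCoach versus App, difference 2.80 points. From Statistical Analysis: 60 per group, two-sided 0.05.

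- Implied SD of change = 4.08 / 0.625 = 6.53.
- Check on the plan's own figure: a two-sample t-test (noncentral t) with 60 per arm and effect size 0.625 gives 92.4%, against the stated 92%.

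**Step 5. Error rate under no true effect.** Noncentrality = (b / 6.53) × √(n/2), with √(60/2) = 5.48.

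| b (points) | b / 6.53 | Noncentrality, n = 60 | Rejection rate, n = 60 | Rejection rate, n = 77 |
|---|---|---|---|---|
| 0.5 | 0.077 | 0.42 | 7.0% | 7.6% |
| 1 | 0.153 | 0.84 | 13.2% | 15.7% |
| 2 | 0.306 | 1.68 | 38.4% | 47.2% |

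The last column uses 292 × 0.8 / 3 = 77.9, taken as 77 per arm. A 1-point shift is 1 / 4.08 = 25% of one planned difference and 1 / 2.80 = 36% of the other.

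**Step 6. What would produce such a shift.** For one youth, a 1 kg error moves %BMIp95 by 100 × (1 / height²) / (95th-percentile BMI). With assumed heights of 1.62 to 1.70 m and an assumed 95th-percentile BMI of 26 to 30 kg/m²:

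- largest: 100 × (1 / 1.62²) / 26 = 1.47 points;
- smallest: 100 × (1 / 1.70²) / 30 = 1.15 points.

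The arm mean moves by this amount times the share of youths with a self-reported baseline, which is not given. If those youths misreport by 1 kg on average in one arm only:

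- share 30%: 0.30 × 1.15 to 0.30 × 1.47 = 0.35 to 0.44 points;
- share 60%: 0.69 to 0.88 points;
- share 100%: 1.15 to 1.47 points.

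**The case against.** The strongest reply is that the list is partly topical and so weak evidence of time order. It has two items numbered 3, an outcomes table in the middle, and steps that run to month 18. The plan calls the consent visit the baseline visit, so surveys may be done the same day. Posting is only to be attempted on the day of consent, and no sentence says the posted scale and tape supply the baseline value. This is fair as to the details. It does not remove item 1a, which ties randomisation to consent and waits for nothing else.

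Several stronger readings are tempting, and the documents do not support them.

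- *That allocation is released at consent for everyone.* Mail consent is excepted, and the moment of disclosure is inferred.
- *That every baseline blood sample follows allocation.* Chart labs can predate it. Labs are also objective, so reporting bias is unlikely.
- *That randomised youths will have no baseline at all.* Eligibility needs a BMI at or above the 85th percentile, so some BMI should normally exist. It is not named as the baseline, however, and for AltaMed referrals it is acquired only if available. Surveys have no such fallback.
- *That every outcome is affected.* Compliance, retention, satisfaction and cost are not changes from a self-reported baseline in this sense, and staff-measured weights are less exposed.
- *That a 1 kg error can be set directly beside 2.80 or 4.08 points.* That error belongs to one person; bias needs an average difference between arms. Misreporting that persists equally at a virtual follow-up would cancel in the change score.

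It also stands that reordering visit 1 leaves untouched the open-label self-report at follow-up.

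**Conclusion.** The point holds in limited form, as an inexpensive improvement that should be made. For in-person and electronic consent, the written rule places randomisation ahead of the baseline surveys and height/weight. For mail consent the order is open. No route makes baseline data a condition of allocation, and handling of a missing baseline is not stated.

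The exposure is greatest for questionnaires and for height and weight self-reported after electronic consent. Neither the direction nor the size of any bias can be derived from the documents. The 7% and 13% error rates show sensitivity to an assumed mean shift of 0.5 or 1 point at 60 per arm with SD 6.53; they do not estimate what happened. With an assumed 30% remote share and a 1 kg average misreport in one arm only, the shift stays below 0.5 points and the error rate therefore below 7.0%.

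**What to change.** Change item 1a so that the surveys and height/weight are completed and locked before the allocation is generated or revealed, and state that the same order applies within the second session for mail consent. For remote youths, send an identical scale and tape to all before allocation, and the arm-specific items afterwards. Obtain chart labs or the research blood draw before allocation where feasible, but do not make them a condition: that would put a trip to CHLA between remote consent and randomisation. State how a randomised youth without a baseline is analysed.

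The cost is a reordered visit, a lock on the randomisation form, a second mailing for remote youths, and a few youths lost before rather than after randomisation. The mail-consent exception shows that deferred allocation is already accepted in this trial.

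The Statistical Analysis section is written in the past tense. If enrolment has closed, report the timing of baseline relative to randomisation by arm and visit mode, count the randomised youths without a baseline, and add a sensitivity analysis limited to staff-measured baselines.

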Up to 404 adolescents (plus 1 parent/youth enrolled) will be recruited for the intervention arms and randomized 1:1:1 via stratified block randomization into one of the following groups: AppCoach, App or Clinic. Demographic information will be collected from all participants. During the intervention period the participants will not attend an inter-disciplinary in-clinic weight management intervention or any other medically supervised weight loss programs. If the participants have underlying comorbidities, they will continue to follow with routine subspecialty providers for standard of care of each underlying condition. Each participant's primary care provider, regardless of the method in which they were recruited (including those recruited from the greater LA county) upon request from participant, will receive a letter from the PI explaining that the individual will be participating in the research intervention during the allotted study period. Parental involvement is not required for those participants randomized to the AppCoach or App group; these participants will complete the intervention independently with the assistance of the coach (if applicable). Parental involvement is required for those participants randomized into the In-Clinic group. Upon completion of the intervention, if the participant was initially referred to a weight management clinic by their primary care provider, they will be offered continued enrollment in the inter-disciplinary weight management clinic for which they were initially referred. In order to further remove barriers to participation, all families who do not have a car will be offered free ridesharing transportation (UBER or Lyft) to- and from CHLA. Additionally, parking validation will be offered for families to park onsite at CHLA for research and/or intervention visits. To increase retention, participants are contacted once per month to maintain engagement. Research staff will provide families with dates of their scheduled assessments/visits. Participants are also given reminder phone calls the day before their assessment/visit.

Trial sites:

A participating trial site must fulfill the following eligibility criteria:

- 1) Have an independent weight management clinic that cares for adolescents.
- 2) The principal investigator and all the clinical research coordinators/staff at the site have been trained on, and understand, the study protocol.

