- 3) The site is within mobile phone range on the other hand, a trial site will be ineligible if it satisfies one or more of the following conditions:
 - 1) The principal investigator withdraws consent for participating in the study.
 - 2) The steering committee of the present trial judges the site to be inappropriate to recruit participants.

Initial trial sites include: CHLA, Los Angeles Biomedical Research Institute at Harbor-UCLA (LA Biomed), UCLA, and Cedars Sinai.

Site Training:

Each on-site CRC will receive 8 hours of training prior to recruitment start date.

Study Design:

404 reflect the 190 youth and 190 parent/guardians plus the 12 youth and 12 parent/guardian subjects that will be enrolled for the pilot study at CHLA.

We are aiming to recruit a total of 292 youth total with 1 parent/legal guardian per youth (total of 584 including the parent/guardian in the subject accrual number + 12 pilot youth + 12 pilot parent/guardian).

We plan to enroll 584 participants (youth & parent/guardian) into each intervention arm as follows:

[figure not shown]
CHLA/AltaMed = 404 (Pilot: 12 youth + 12 parent/guardians; Open enrollment: 190 youth & 190 parent/guardians)

UCLA = 60 (30 youth & 30 parent/guardians)

Harbor UCLA = 60 (30 youth & 30 parent/guardians)

Cedars Sinai = 60 (30 youth & 30 parent/guardians)

Pilot Group: We plan to initially recruit 12 patients from the CHLA EMPOWER clinic. The patients will be randomized to the three intervention arms and will complete a 2-month trial to assess intervention fidelity of the curriculum and identify any potential difficulties. The pilot subjects are reflected in the information above. .

Assessments:

Anthropometric Data

Height and weight will be assessed at in-person visits by study team member or self-reported if visit is conducted virtually via WebEx. Height will be measured using a Quick Medical stadiometer, accurate to 0.1 cm (Quick Medical, Issaquah, WA). Weight will be measured on a self-calibrating Mobile Stand Digital Scale,

accurate to 0.1 kg. Participants will wear minimal clothing during the height and weight measurements. BMI will be calculated as kilograms per square meter and BMI Z-score (zBMI) and percent over the 95th percentile (%BMI_{p95}) will be determined utilizing the CDC growth charts.

Physical Activity

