Twelve participants (and one of their parent/guardian) will be recruited from CHLA to complete a pilot intervention starting 2 months before the initial open recruitment commences. The youth participants will be randomized to one of the three arms and complete that intervention accordingly. The team members will continue to be monitored as they implement the intervention and barriers to execution will be evaluated. Those 12 participants will complete the full study period. If not protocol amendments are made they will be included in the final analysis, if protocol amendments are made they will be excluded.

Intervention Compensation:

Traditional payment: Payments will be provided at the end of study visits at months 3, 6, 12, and 18 as shown in the table below. Monthly payment: The participant may elect to receive compensation at monthly intervals for the first 6 months if desired. If this method is selected, the participant will provide the study team with their email address and a gift card will be emailed to them monthly based upon how much of the intervention they participate in or they can opt for the study team to email them images of the gift cards.

Each youth participant, regardless of which group they are assigned to, will receive compensation in the form of gift cards. Each youth participant has the opportunity to earn up to a total of \$200 for participation in this study. The amount of payment will be based upon how much intervention adherence occurs. The amount will be rounded to the nearest ten-dollar increment, by rounding up.

Parents/guardians will not be paid for their participation in this study.

For Group 1 (AppCoach) and 2 (App):

The app will automatically accrue points as the participant interacts with the app components. They will receive a pre-determined amount of points each time they open the app, each time they weigh in, each time they log a problem food, etc. The participants will be able to enter the motivation section of the app as desired to evaluate

how many points they have accrued. In addition, lack of participation with the app results in loss of points which will result in decreased financial gain. This balance is also available to the participants in real time. Points will be associated with financial quantity (1 point = 5 cents) and the youth participants will earn compensation as they complete the intervention as directed.

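### The ceiling of 404 adolescents is one site's youth-plus-parent count (the trial total is 292 youths), and an open-ended amendment rule decides whether the 12 randomised pilot youths are analysed

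*Combined protocol and SAP*

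**What the plan says.** **Youths to be randomised.** Enrollment and Retention gives "Up to 404 adolescents (plus 1 parent/youth enrolled) will be recruited for the intervention arms and randomized 1:1:1". The Study Design section that follows Site Training explains the same number differently: "404 reflect the 190 youth and 190 parent/guardians plus the 12 youth and 12 parent/guardian subjects". Its site list repeats the split as "CHLA/AltaMed = 404 (Pilot: 12 youth + 12 parent/guardians; Open enrollment: 190 youth & 190 parent/guardians". The other three sites have identical rows, for example "UCLA = 60 (30 youth & 30 parent/guardians". That section also states a target of 292 youths with one parent each. Power and Sample Size Estimates and Feasibility both use 292.

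**The overall total.** Study Design writes 584 and follows it with plus signs and 12 pilot youths and 12 pilot parents. It then says "We plan to enroll 584 participants (youth & parent/guardian) into each intervention arm", which introduces the site list. The Pilot Group paragraph closes by saying that the pilot subjects are already counted in the figures before it.

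**The pilot.** Under Pilot Group, the 12 patients are randomised to the three arms and "will complete a 2-month trial to assess intervention fidelity of the curriculum". Under Pilot Sessions, "Those 12 participants will complete the full study period". That section keeps them in the final analysis if there is no protocol amendment, but "if protocol amendments are made they will be excluded".

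**Analysis principle.** Statistical Analysis says that analyses followed intention-to-treat.

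**The concern.** Two things are at stake.

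The first is the accrual ceiling. An ethics committee, a monitor or the sponsor will read the enrolment sentence as the maximum number of minors to be randomised. As written, it takes a head-count of youths and parents at one site, relabels it as adolescents for the whole trial, and then adds a parent to each again.

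The second is the analysis set. The pilot youths are randomised. Whether they are analysed depends on whether the protocol is later amended, which the study team decides. No type of amendment and no cut-off date is given, so on its wording an administrative change late in the trial would trigger exclusion. The only blinding described is of block size, and the Data Collection Management Plan gives investigators ongoing access to weight data from the app. The plan therefore has no safeguard against the trigger falling after outcomes are known.

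**Working it through.** **1. Reproduce the plan's own totals** (inputs: site rows in Study Design)

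- CHLA/AltaMed people: 190 + 190 + 12 + 12 = 404, of whom 190 + 12 = 202 are youths.
- All sites, people: 404 + 60 + 60 + 60 = 584.
- All sites, youths: 202 + 30 + 30 + 30 = 292, and 2 × 292 = 584.

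Both 404 and 584 reproduce, with the pilot inside each. Youths per arm: 292/3 = 97.3.

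**2. Enrollment and Retention taken literally**

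- Youths: 404, or 404/3 = 134.7 per arm.
- With one parent each: 404 × 2 = 808 people, against 584.
- Excess youths: 404 − 292 = 112; 112/292 = 38%.

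**3. Analysis set under the amendment rule**

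- No amendment: 292 youths before dropout.
- Amendment: 292 − 12 = 280, or 93.3 per arm.
- Difference: 12/292 = 4.1%.

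**4. Does the difference matter for power?** Inputs are the effect sizes, the two-sided 5% level and the 20% dropout in Power and Sample Size Estimates. Aim 1 uses the noncentral F distribution with three groups and noncentrality N·f². Aims 2 and 3 use the noncentral t distribution with n per arm and noncentrality d·√(n/2). After dropout, N is 292 × 0.8 = 233.6 or 280 × 0.8 = 224.

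| Comparison | Effect size | Pilot kept (233.6) | Pilot dropped (224) |
|---|---|---|---|
| Aim 1, zBMI | f = 0.244 | 92.3% | 91.1% |
| Aim 1, %BMIp95 | f = 0.263 | 95.6% | 94.8% |
| Aim 2, zBMI | d = 0.580 | 94.9% | 94.1% |
| Aim 2, %BMIp95 | d = 0.625 | 97.2% | 96.7% |
| Aim 3, zBMI | d = 0.464 | 82.0% | 80.4% |
| Aim 3, %BMIp95 | d = 0.452 | 80.0% | 78.3% |

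The largest loss is 1.7 percentage points. Aims 1 and 2, the only ones for which the plan claims 80%, stay above 91%. The plan's stated powers (83, 89, 88, 92, 71 and 68%) are lower than these because they correspond to 60 per arm (83.6, 89.0, 88.3, 92.4, 71.3 and 69.0%) and not to 292. That is a separate matter.

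**5. Pilot texts side by side**

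| Pilot Group | Pilot Sessions |
|---|---|
| A 2-month trial to check fidelity | Starts 2 months before open recruitment; the 12 complete the full study period |
| Nothing on use of the data | Kept or dropped according to whether amendments are made |

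Post Study Follow-up Options puts the study period at 18 months.

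**The case against.** The best defence is that the correct number is easy to recover. Only one sentence says 404 adolescents; the stated target, the site rows, the power section and Feasibility all give 292. Each site has an explicit allocation, so no site would be misled about its own share. This stands, and it limits the error to the overall ceiling. It does not remove it, because the enrolment sentence is where a reader looks for that ceiling.

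Several stronger readings are tempting, but the documents do not support them:

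- *304 youths (608 people).* This rests only on the plus signs after 584. The site rows and the closing sentence of the Pilot Group paragraph place the pilot inside the total.
- *584 per arm, or 1,752 people.* The phrase introduces a site list that sums to 584 overall. The wording is loose and no such plan exists. A figure missing from the extracted text may have shown the arm split.
- *Double enrolment at CHLA.* The enrolment sentence sets no CHLA cap, and the site row splits 404 explicitly.
- *A pilot with no 6- or 18-month outcome.* The 2-month trial can be read as the lead-in described under Pilot Sessions. The two texts need reconciling, but the least favourable reading is not established.
- *Underpowering.* The dropout allowance is about 58 youths (292 × 0.2 = 58.4), far more than 12, and 292 was an enrolment figure, never the number expected to complete.

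On the amendment rule, the defence is that it follows directly on the evaluation of pilot barriers, so amendments arising from the pilot are the natural meaning. That is a fair guess at intent, but the text does not say so. Equally, nothing shows that the rule was or will be used late or with outcomes in view. The defect is that it permits this.

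**Conclusion.** The 404 is a definite error: the trial's youth total is 292, and the enrolment sentence exceeds it by 112 youths (38%). This rests only on the plan's own site rows.

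The amendment rule is a real design defect of modest numerical size. It leaves the analysis set at 292 or 280 before dropout, contingent on a post-randomisation event under the team's control, and so conflicts with intention-to-treat. A reader might infer that the analysed number is wrong, or that the pilot must be left out whatever happens. The first goes too far, because the number is undetermined between two values. The second is a preference: either choice is defensible if fixed without outcome knowledge.

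The wording around 584 and the two accounts of the pilot's length are inconsistencies to be reconciled. The power consequence is negligible, assuming the plan's effect sizes and 20% dropout.

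**What to change.** - **Enrollment and Retention:** replace 404 adolescents with 292 youths in total, about 97 per arm: 202 at CHLA including the 12 pilot youths, and 30 at each of the other three sites.
- **Study Design:** say that 584 is the overall youth-plus-parent total including the pilot, remove the plus-sign addition, and delete the reference to each intervention arm.
- **Pilot Group and Pilot Sessions:** reconcile the two statements of how long pilot participants are followed.
- **Pilot Sessions:** replace the open trigger with a rule that does not depend on outcome knowledge. For example, exclude only for amendments that arise from the pilot and change the intervention, eligibility or outcome measurement, with the decision recorded before open enrolment. Statistical Analysis is written in the past tense, so if that point has passed, state which amendments were made, when, and how the rule was applied.
- **Statistical Analysis:** report the primary result both with and without the 12 pilot youths.

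The cost is protocol wording and one extra sensitivity analysis. If the pilot is excluded, the primary set loses 12 youths (4.1%) and at most 1.7 points of power in the table above.
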